5. STUDY OBJECTIVES

The objectives of this study are to describe the safety and immunogenicity of ALVAC-HIV (vCP205) administered via 2 alternative delivery routes in an effort to improve the immunogenicity of this vaccine candidate as defined by improved cellular immune responses. It is a Phase I description of the acute safety and immunogenicity of ALVAC-HIV (vCP205) transfected autologous DC, or ALVAC-HIV (vCP205) delivered by the intradermal route. The internal referent will be the standard method of delivery via the intramuscular route. This will be the first study of vCP205 delivered ID or via autologous dendritic cells in HIV-seronegative humans.

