This study will provide new, preliminary data regarding the respective immunogenicities of intradermal and *ex vivo* DC immunization with vCP205 relative to the moderately immunogenic IM route in normal human volunteers. The study is not designed to resolve the null hypothesis.

			Months			
Group	Vaccine/	Subcutaneous	0	1	3	6
	Placebo*	Route				
Ι	8/4	DC	DC-vCP205 KLH pulsed or KLH pulsed DC only	DC-vCP205 or DC only	DC-vCP205 or DC only	DC-vCP205 or DC only

Subcutaneous Administration of vCP205 via transfected, autologous dendritic cells

Vaccine = vCP205 transfected DC pulsed with KLH, *Placebo = DC pulsed with KLH only (control DC) delivered in 2 x 0.2 ml subcutaneous injections. The KLH is used in the first vaccination only. $vCP205 = \sim 10^{6.5} \text{ TCID}_{50} (1 \text{ vial})$ reconstituted in1 ml sterile water/ 2-3 x 10^{6} DC

Intradermal or Intramuscular Administration of vCP205 via injection

			Months			
Group	Vaccine/ Placebo ¹	Route	0	1	3	6

II	8/4	Intradermal	vCP205	vCP205	vCP205	vCP205
III	8/4	Intramuscular	vCP205	vCP205	vCP205	vCP205

 $ID = \sim 10^{6.5} TCID_{50} (1 \text{ vial})$ reconstituted in 1 ml sterile water, delivered in 4 x 0.125 ml intradermal injections (0.5 ml total dose).

 $IM = \sim 10^{6.5} TCID_{50}$ (1 vial) reconstituted in 1 ml sterile water, delivered in a single 1 ml intramuscular injection (1.0 ml total dose).

 1 Placebo = sterile saline

6.2 Rationale for the Study Arms:

Group I. Delivery of ALVAC-HIV vCP205 to autologous *ex vivo* generated DC. We will directly target the dendritic cell as a means of maximizing the antigen presentation of encoded HIV-1 genes within the vaccine vector. Theoretically, this arm would serve as the optimal antigen delivery method in this descriptive study. It will provide important conceptual information on the benefits of directly loading critical antigen presenting cells with vectors for HIV vaccine development. If the results indicate beneficial effects of directly targeted-DC, this type of study will lay the groundwork for future vaccine development with an emphasis on *in vivo* DC targeting. We will include the use of KLH as a control antigen in this arm (for the first injection only) as means of quality control to ensure that the canarypox transfection process is not inhibitory for DC function in some way. We can then reasonably use the anti-KLH (primary) immunity that would develop in the control DCs as an internal referent for this arm.

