6.7 Procedural Flow Chart

6.8 Volunteer's Vaccine Schedule

6.9 Statistical Methods and Determination of Sample Size

6.9.1 Statistical Plan: Design and Sample Size Calculation

The data will be analyzed by DCAC. Any data analyses carried out independently by investigators should be submitted to WRAIR before publication or presentation.

The trial as designed has 3 groups:

Group I: Subcutaneous reinjection of *ex vivo* generated vCP205 transfected autologous dendritic cells Groups II and III: Intradermal or intramuscular injection of vCP205

The primary safety measurements include data from the clinical laboratory tests, observed immunization reactions (local and systemic) and adverse events. The primary immunogenicity data focus on cellular responses which will be assayed by both blastogenesis (lymphocyte proliferation) and cell mediated cytotoxicity.

This study is intended as a proof-of-concept to test the safety of the dendritic cell and ID delivery routes. It is not a definitive hypothesis testing study aimed at evaluating the relative immunogenicities (as measured by CTL response) of the IM, ID and DC arms. Despite this, we were able to determine the power with which differences between the DC arm and the better of the IM or ID arms could be detected. Assuming 100% (8 of 8) CTL response in the DC arm and 38% (3 of 8) response in the IM or ID arm, we would have approximately 70% power to detect a true difference in CTL response between the two arms if one actually exists. Additional information provided by immunomonitoring using ELISPOTs and intracellular flow cytometry (for IFN-gamma production) and blastogenesis assays (lymphocyte proliferation), we believe, will allow the study to determine if DC or ID routes are substantially better than the IM route.

All subjects receiving at least one injection of vaccine will be included in the safety and tolerability analyses. All data exclusions, including premature terminations, will be detailed and tabulated according to vaccine group. Data listings will include all subjects.

Demographic data obtained during the baseline visit will be listed for each subject. Summary statistics will be tabulated for each vaccine group. Subjects will be assessed for comparability at baseline. Descriptive statistics will be presented for continuous variables (age, height, weight). Frequency counts and percents will be presented for categorical variables (age, sex, and race).

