6.9.3 Immunogenicity

Lymphocyte proliferation will be described as a stimulation index (LSI = CPM of test antigen/Medium Control). For each group geometric mean LSI, median minimal and maximal LSI, as associated 95% confidence intervals will be calculated. The primary timepoint of interest for antibody responses will be one month post immunization #4; cellular responses will be measured as described in section 6.7. The following definitions establish discrete categorical data (response present vs absent) for significance testing:

Cellular: A positive lymphoproliferative response is present if an $LSI \ge 5$ to an HIV-specific vaccine component develops at 2 timepoints post vaccination.

A CTL response is present if HIV-antigen specific lysis at two effector: target (E:T) ratios is > 10%. The response is CD8+ T cell mediated if, on subsequent testing (depletion assay), depletion of CD8+ T cells removes 50% of the HIV antigen specific lytic activity, while removal of CD4+ cells maintain at least 5% HIV specific lysis. Likewise, The response is CD4+ T cell mediated if, on subsequent testing, depletion of CD4+ T cells removes 50% of the specific lytic activity, while removal of CD8+ T cells maintain at least 5% specific lysis.

Cumulative % bulk CTL response is calculated as follows: number of participants with a CTL response to any vaccine component on any study day/total # of participants X 100 (for vaccine and placebo groups). Cumulative % CD8+ T cell mediated CTL response is calculated as follows: number of participants with a CD8+ T cell specific CTL response to any vaccine component on any study day/total # of participants X 100 (for vaccine and placebo groups). CTL responses will be categorized for the purpose of enumeration as: 1) high response, occurring on 5 or more occasions in an individual during the study, 2) medium response, occurring on 3-4 occasions and 3) low response, occurring on 1 or 2 occasions.

ELISPOT assay:

The number of cytokine (IFN-g or other) spot forming cells $(SFC)/10^6$ PBMC will be assessed to HIV vaccine components. Responses are calculated by subtracting the background SFC (in response to media alone) from the # of SFC to HIV vaccine components.

A positive **ELISPOT** response is defined by an absolute number of SFC

> 20 SFC/10⁶ PBMC and SFC to HIV vaccine components at least twice those of background.

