Humoral: A positive neutralization response is defined as >50% reduction in HIV gag antigen (vaccine related HIV strains vs normal human serum) in a continuous T cell line based neutralization assay

For each group, least squares geometric mean titer (GMTs), associated 95% confidence intervals, and median, minimal and maximal titer will be calculated to MN, LAI, gp120/160 antigens, by ELISA. Neutralizing antibody titer will be similarly measured to TCLA viruses and to select primary isolates.

Chi-square and Fisher's exact tests will be employed. All tests will be conducted as two-sided at the 0.05 significance level. Statistically significant results will be annotated by their degree (*p<0.05;**p<0.01;***p<0.001).

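### Section 6.9.1 gives about 70% power for DC versus the better of IM or ID, but by Fisher's test that contrast has about 42% (DC versus IM about 65%), and ID versus IM has too little power to determine anything

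*Protocol*

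**What the plan says.** Protocol Section 6.9.1 presents the trial as a proof of concept and not a definitive test of relative immunogenicity. It then says the authors could still work out how well "differences between the DC arm and the better of the IM or ID arms could be detected". The inputs are a CTL response in 8 of 8 DC vaccinees and in 3 of 8 (printed as 38%) in the IM or ID arm. The result is given as about 70% power. The paragraph ends with the belief that ELISPOT, intracellular flow cytometry and proliferation data "will allow the study to determine if DC or ID routes are substantially better than the IM route".

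Other sections bear on this:
- Section 5: "The internal referent will be the standard method of delivery via the intramuscular route".
- Section 6.1: "The study is not designed to resolve the null hypothesis".
- Section 6.9.3, before the responder definitions: "The following definitions establish discrete categorical data (response present vs absent) for significance testing".
- Section 6.9.3, on the tests: "Chi-square and Fisher's exact tests will be employed", and "All tests will be conducted as two-sided at the 0.05 significance level".
- Section 4 expects a CTL rate of roughly 30 to 50% with IM, a better response with ID and the best response with DC. It gives no rate clearly attached to ID.

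**The concern.** The power sentence and the conclusion sentence stand in one paragraph but use different comparators. Taken literally, the first compares DC with whichever of two arms turns out better. The second is two comparisons with IM: DC versus IM and ID versus IM. Beating the better of two arms is harder than beating one arm chosen in advance, so a single power figure cannot serve both.

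Two things are at stake. First, a reader who relies on the 70% may be relying on a figure that belongs to neither contrast. Second, the protocol promises an answer on ID versus IM without giving any power for it. If 8 versus 8 cannot separate plausible rates, a non-significant ID result says almost nothing, yet the wording invites the reader to take it as settled. That also runs against the protocol's own statement that it is not designed for hypothesis testing.

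**Working it through.** **Inputs.** There are 8 active recipients per arm (Protocol Summary; Section 6.5.3). CTL rates are DC 100% and comparator 3/8 = 37.5%, printed as 38% (6.9.1). Tests are two-sided at 0.05 (6.9.3). I take Fisher's exact test as the main case because cell counts are small, and return to chi-square under the objection. All 8 per arm are assumed evaluable. ID rates above 37.5% are my assumptions.

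**Step 1: which results are significant.** With DC at 100%, DC is always 8/8. The two-sided Fisher p-values are:
- 8/8 vs 3/8: 2 × C(8,3)/C(16,11) = 2 × 56/4368 = 0.0256, significant.
- 8/8 vs 4/8: 2 × C(8,4)/C(16,12) = 2 × 70/1820 = 0.0769, not significant.

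So DC beats a comparator arm only if that arm has 3 responders or fewer.

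**Step 2: the plan's figure, one fixed comparator.** Power = P(X ≤ 3) with X ~ Binomial(8, 0.375) = 0.0233 + 0.1118 + 0.2347 + 0.2816 = **0.651**. At 0.38 it is 0.640. The stated 70% is not reproduced. Fisher gives 70.6% only if the comparator rate is 35%. Other methods at 37.5%, one fixed comparator:

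| Method | Power |
|---|---|
| Chi-square, Yates-corrected | 65.1% |
| Chi-square, uncorrected (exact enumeration) | 86.3% |
| Normal approximation, pooled | 84.1% |
| Normal approximation, continuity-corrected | 60.5% |
| Arcsine, continuity-corrected | 66.3% |

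**Step 3: the contrast the sentence names.** DC beats the observed better of IM and ID only if both have 3 responders or fewer. The arms are independent, so power is the product P(X_IM ≤ 3) × P(X_ID ≤ 3):
- IM = ID = 37.5%: 0.651 × 0.651 = **0.424**.
- IM = ID = 38%: 0.640 × 0.640 = 0.410.
- IM 37.5%, ID 50%: 0.651 × 0.363 = 0.237.
- IM 37.5%, ID 62.5%: 0.651 × 0.137 = 0.090.

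**Step 4: ID versus IM.** At 8 versus 8, Fisher is significant only when the counts differ by 5 or more (5 v 0, 6 v 1, 7 v 2, 8 v 3, and so on). Power is therefore the sum over IM counts b of P(IM = b) × P(ID ≥ b + 5), plus the mirror image. For ID at 75% and IM at 37.5%:

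0.0233 × 0.886 + 0.1118 × 0.679 + 0.2347 × 0.367 + 0.2816 × 0.100 = 0.0206 + 0.0759 + 0.0861 + 0.0282 = 0.211. The mirror term is below 0.001.

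| Assumed ID rate (IM 37.5%) | Power, Fisher |
|---|---|
| 50% | 3.6% |
| 62.5% | 9.5% |
| 75% | 21.1% |
| 87.5% | 39.7% |

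**The case against.** **The power sentence may be loosely worded.** The better arm may simply mean whichever arm truly responds better, assumed to be at 38%. Section 6.9.3 plans no test against the observed better arm, and IM is the fixed referent in Section 5 and in the conclusion sentence. This stands in part. On that reading the relevant figure is 64 to 65%, only some 5 to 6 points below the statement. The sentence still needs rewording, because it does not say this and does not name IM.

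**Chi-square is also named.** Uncorrected, it already rejects at 8/8 vs 4/8 (p = 0.021). The fixed-arm power is then 86.3%, and the better-of-two power is 0.863 × 0.863 = 74.4%, not far from 70%. So the 42% and 65% hold for Fisher, and for Yates-corrected chi-square, which has the same cut-off. The protocol does not say which test underlies its figure. Uncorrected chi-square is a poor basis here: in the 8/8 vs 4/8 table the expected number of non-responders is 2 per arm, and its true size at 37.5% is 6.7%.

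**The conclusion sentence is hedged as a belief and rests on the extra assays.** True, but no power is given for those assays. The only tests named are Fisher and chi-square on responder status, again with 8 versus 8.

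**Stronger readings.** A reader might infer that the same data can support opposite conclusions. They cannot: a significant DC-IM result beside a non-significant DC-ID result answers two questions, and no direction is reversed. A reader might also infer a multiplicity failure. On CTL alone, three pairwise Fisher tests at null rates of 30 to 50% give a family-wise error of only 3 to 6%. Contrast order and alpha control may also stand in an analysis plan that is not at hand.

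**Conclusion.** The concern holds as an internal mismatch with a measurable size. By two-sided Fisher at 0.05, the stated 70% power is about 65% for DC versus one fixed arm and about 42% for the contrast the sentence names when IM and ID are equal. It falls to 24% or 9% if ID is truly 50% or 62.5%. The claim that the study can determine whether ID is substantially better than IM is not supported, with power of roughly 4 to 21% for ID rates of 50 to 75%. That claim also conflicts with Section 6.1 and with the opening of the same paragraph in 6.9.1.

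These figures assume a true DC rate of exactly 100% and no loss of evaluable subjects. Both are favourable: Section 6.4.3 limits the final immunogenicity analysis to subjects with all four injections and the Visit 11 draw, so real power is likely to be lower.

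The documents do not support going further, to a required testing hierarchy or to demoting proliferation, ELISPOT or flow cytometry. The protocol lists these as primary measures in a descriptive Phase I study.

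**What to change.** In Section 6.9.1:

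1. Remove the reference to the better of the two arms. State the power for DC active versus IM active on CTL response: about 65% (Fisher's exact test, two-sided 0.05, 8 versus 8, DC 100%, IM 37.5%).
2. Replace the closing claim that the study can determine superiority. Say instead that it will describe the DC-IM and ID-IM differences in response rates with exact 95% confidence intervals. This agrees with Sections 5 and 6.1.

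The cost is a slightly less favourable power figure and a softer claim. No subjects, samples, assays or primary measures change.

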6.9.2 Safety

All subjects receiving an injection of vaccine or placebo will be included in the safety and tolerability analyses.

6.9.2.1 Postimmunization Reactions (Local and Systemic)

The maximal severity of local and systemic postimmunization reactions occurring in the seven days following each immunization and any immunization will be tabulated by group. Local reactions tabulated will include: injection site pain, erythema, induration, and temperature. Systemic reactions reported within seven days postimmunization will include: chills, nausea, malaise, myalgia, arthralgia, headache, rash and fever (as described in Toxicity Grading Scale, p. 58). Additionally, pain on injection will be noted. Frequencies and percentages of subjects experiencing each reaction will be presented for each symptom severity. If a reaction occurs more than once for a subject, the reaction will be classified according to the highest occurring severity and closest vaccine relationship.

Summary tables showing the occurrence of any local or systemic reaction overall and at each time point will also be presented.

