6.6.2.2 Stopping Criteria

A severe adverse event or grade III/IV toxicity which is probably or definitely related to vaccination will result in discontinuation of vaccination for the individual. The volunteer will be asked to continue the follow-up schedule for the duration of the study.

Two severe adverse events or grade III/IV toxicity which are probably or definitely related to vaccination will result in discontinuation of the study arm. The volunteers will be asked to continue the follow-up schedule for the duration of the study.

Discontinuation of a study arm will prompt an immediate analysis of study safety data for all arms, a review of available immunogenicity data and consideration of modifying the design of the discontinued study arm (i.e.dose reduction) to minimize the risks to participants in the modified arm. New volunteers would be recruited for the modified study arm.

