Serious (Grade 4):	Life threatening
Death (Grade 5):	

The *relationship of immunization* to adverse event (AE) will also be determined by the investigator, based on the following definitions:

Not Related:

AE obviously explained by another cause; OR The time of occurrence of AE is not reasonably related to vaccination.

Remotely Related:

AE more likely explained by causes other than vaccination.

Possibly Related:

Vaccine administration and AE occurrence reasonably related in time; AND AE explained equally well by causes other than vaccination.

Probably Related:

Vaccine administration and AE occurrence reasonably related in time; AND AE more likely explained by vaccination than by other mechanisms.

Definitely Related:

Vaccine administration and AE occurrence reasonably related in time; AND Vaccination most likely explains the AE; AND AE is consistent with pattern of vaccine-related events.

The definition of a serious adverse event is as follows:

A serious adverse event is defined as any untoward medical occurrence that:

-Results in death.

-Is life threatening (i.e., the patient was, in the opinion of the Investigator, at immediate risk of death from the event as it occurred).

-Requires or prolongs inpatient hospitalization (elective hospitalization excluded).

-Results in persistent or significant disability/incapacity, (i.e., the event causes a substantial disruption of a person's ability to conduct normal life functions).

-Is congenital anomaly/birth defect of a pregnancy arising while on study

-Is an important and significant medical event that, based upon appropriate medical judgment, may jeopardize the patient or subject and may require medical or surgical intervention to prevent one of the other outcomes defining serious. Written follow up information will be provided, when available, for all serious and unexpected adverse events in addition to the initial reports.

All unexpected adverse events (AE) will be reported to the WRAIR HURC and the HSRRB within 7 days. All deaths and any other serious adverse event will be reported to the FDA and the WRAIR

HURC and the HSRRB within 24 hours regardless of the perceived relationship with the vaccine. All other AE and SAE will be reported in accordance with all applicable regulations. Reports are made by telephoning the Secretary of the IRB and one of the following:

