6.9.2.2 Other Adverse Events

The original terms used by investigators on the CRF will be translated to COSTART terms and grouped into body system and presented as frequency tables. For each and any immunization, the number and percent of subjects with adverse events will be tabulated, by group and by site. When adverse events occur more than once, the maximal severity and relationship to vaccine will be counted. Three summaries will be generated: (1) Serious adverse events (SAEs); (2) adverse events that are definitely, probably or possibly related to vaccination, and (3) adverse events that are remotely or not related to vaccination. Data listings of all adverse events will be provided by subject, as will subset listings summarizing subjects withdrawn from the study because of an adverse event.

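### A recurring adverse event is classified by separate maxima of severity and relationship, so the any-immunization summaries can show a pairing that no occurrence had and lose the unrelated occurrence

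*Protocol*

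**What the plan says.** Two sentences in the protocol fix how repeats are counted. For post-immunization reactions, section 6.9.2.1 states that "the reaction will be classified according to the highest occurring severity and closest vaccine relationship". For other adverse events, section 6.9.2.2 states: "When adverse events occur more than once, the maximal severity and relationship to vaccine will be counted". Neither says that the severity and the relationship must belong to the same occurrence.

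The planned output differs between the two streams. For reactions, section 6.9.2.1 says: "Frequencies and percentages of subjects experiencing each reaction will be presented for each symptom severity". It names no breakdown by relationship. For other adverse events, section 6.9.2.2 plans a summary of serious events and two summaries split by relationship: "adverse events that are definitely, probably or possibly related to vaccination" and "adverse events that are remotely or not related to vaccination". Both sections tabulate for each immunization and for any immunization. Section 6.9.2.2 also says: "Data listings of all adverse events will be provided by subject".

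Relationship is judged event by event on a five-level scale (section 6.6.2.3). Two occurrences of one term in one volunteer can therefore carry different relationships.

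**The concern.** Severity and relationship describe a single event. If each is maximised separately over a volunteer's occurrences, the result may describe no event that took place. With four immunizations over six months, a term can recur, and an investigator may judge one episode related and another not.

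Two distortions follow in the relationship-split summaries. The related summary can inherit a severity from an unrelated episode. The unrelated summary loses a volunteer who did have an unrelated episode, because that volunteer is now counted only at the closest relationship. Adverse events are among the primary safety measurements, and section 6.9.1 gives testing the safety of the dendritic-cell and intradermal routes as the purpose of the study. With 8 active recipients per arm, one misplaced volunteer is visible in a percentage.

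**Working it through.** The plan states no figure for this rule, so there is none to reproduce. The check applies the rule to a minimal case, follows the result into the planned tables, and then shows its size under stated assumptions.

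**1. Minimal case.** Take one volunteer, one COSTART term and two occurrences, both recorded on the adverse event form (invented data). Relationship is scored from 1 (not related) to 5 (definitely related), following the levels in section 6.6.2.3.

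| | Severity | Relationship |
|---|---|---|
| Occurrence A | Grade 3 | 1, not related |
| Occurrence B | Grade 1 | 4, probably related |
| Rule as written | max(3, 1) = 3 | max(1, 4) = 4 |

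The volunteer is classified as Grade 3, probably related, which is neither A nor B. A same-occurrence reading does not rescue the sentence: A has the highest severity but not the closest relationship, and B the reverse, so no single occurrence meets both conditions. If severity is instead linked to relationship, the volunteer counts at Grade 1 in the related summary and at Grade 3 in the other.

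**2. Where the result lands.**

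| Output | Effect |
|---|---|
| Solicited reactions (6.9.2.1) | None: table is by severity alone, and a maximum severity is a correct marginal summary |
| Other adverse events, related summary, any immunization (6.9.2.2) | Volunteer can carry the severity of an unrelated occurrence, if severity is shown |
| Other adverse events, remotely or not related summary, any immunization (6.9.2.2) | Unrelated occurrence is lost, whether or not severity is shown |
| Summaries for a single immunization | Affected only if the term recurs after that one immunization |
| Stopping criteria (6.6.2.2) | None: they do not read the tables |

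The false pairing needs occurrences that differ in both severity and relationship. The loss from the unrelated summary needs only that one occurrence is at least possibly related and another is not.

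**3. Weight of one volunteer.** The group sizes are 8 active and 4 control (Protocol Summary). One volunteer is 1/8 = 12.5 percentage points of an active arm, and 1/12 = 8.3 points of a whole group.

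**4. Illustration under assumptions.** Let a volunteer have k occurrences of one term. Each is severe with probability s and related with probability r, independently of each other and across occurrences. The values of k, s and r and the independence are assumed; none comes from the protocol.

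- Counted as severe and related under separate maxima: 1 − (1−s)^k − (1−r)^k + [(1−s)(1−r)]^k
- At least one occurrence that is itself severe and related: 1 − (1 − sr)^k

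| k | s | r | Separate maxima | Same occurrence | Ratio |
|---|---|---|---|---|---|
| 2 | 0.05 | 0.7 | 8.9% | 6.9% | 1.29 |
| 2 | 0.05 | 0.3 | 5.0% | 3.0% | 1.67 |
| 2 | 0.10 | 0.5 | 14.3% | 9.8% | 1.46 |
| 4 | 0.10 | 0.5 | 32.2% | 18.6% | 1.74 |
| 4 | 0.05 | 0.3 | 14.1% | 5.9% | 2.40 |

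For k = 2, s = 0.05, r = 0.3: 1 − 0.9025 − 0.49 + 0.4422 = 0.0497, against 1 − 0.985² = 0.0298.

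These shares apply only to volunteers who already have k occurrences of one unsolicited term. They show the direction and how it grows with recurrence. They do not estimate what this trial would see.

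**The case against.** **No table crossing severity with relationship is specified.** This stands in part. Section 6.9.2.2 does not say that severity appears inside the related summary, so the false pairing depends on the table layout. The loss from the unrelated summary does not, because that summary is itself defined by relationship.

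**Solicited reactions.** A reader might infer that the reaction tables will report severe related reactions that never happened. The documents do not support this. Section 6.6.2.3 sends reactions within 7 days to a reactogenicity form and everything else to the adverse event form, and the split by relationship is planned only for the second stream. Per-dose rates typical of solicited symptoms are therefore no guide to the size of the problem.

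**Stopping rules.** A reader might also infer that the rule could trigger or mask stopping, since both use severity and relationship. Section 6.6.2.2 is worded for the event itself: "A severe adverse event or grade III/IV toxicity which is probably or definitely related to vaccination will result in discontinuation of vaccination for the individual". Likewise, the arm-level criterion counts events, not table entries.

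**Bias between routes.** The illustration grows with recurrence, which suggests a distorted comparison of arms. The protocol gives no reactogenicity rates by route and section 6.9.2 plans no between-arm safety test, so this cannot be shown.

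**Conservatism and listings.** For the related summary the error overstates harm, and the by-subject listings let anyone trace it among 36 volunteers. Both points are fair and keep this minor. They do not correct the summary tables, and the unrelated summary errs in the other direction, by omission.

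**A matter for the SAP.** Table conventions often sit there, and no SAP was available. But the protocol does not leave a gap here; it states a rule, and for discordant occurrences that rule has one workable reading.

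**Conclusion.** The point holds in a limited form. As worded, the rule takes severity and relationship separately, and this matters in the any-immunization summaries of other adverse events when a volunteer's occurrences of one term disagree. There it can raise the severity shown for a related event and remove an unrelated one from its summary. One affected volunteer is 12.5 percentage points of an 8-person active arm.

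The expected number of affected volunteers is unknown and may be none. Under the assumed values above, the share counted as severe and related is overstated by a factor of about 1.3 to 2.4 among volunteers with repeats, but that range rests wholly on assumed rates and on independence. This is a small wording defect in a primary safety summary. It does not show that the safety tables as a whole are wrong.

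**What to change.** In section 6.9.2.2, replace the counting sentence with a linked rule:

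- **Related summary:** count each volunteer once per term, at the maximal severity among occurrences judged definitely, probably or possibly related.
- **Remotely or not related summary:** count each volunteer once per term, at the maximal severity among those occurrences. A volunteer may appear in both summaries.
- **All-causality table:** add one, with each volunteer counted once per term at maximal severity.

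In section 6.9.2.1, apply the same linkage to any reaction table that shows relationship. The table by severity alone can stay as it is.

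The cost is the wording of two sentences and a programming rule; no new data are needed. There are two downsides. Because a volunteer can appear in both summaries, their counts no longer add up to the total, which a footnote should say. The related table also becomes slightly less conservative than under separate maxima.
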